#### **8.1.7. Clinical Safety Laboratory Assessments**

Clinical safety laboratory assessments will be performed at screening, on Day -1 (Pre-V1), and throughout the study at timepoints specified in the SoA (Section 1.3).

Blood samples for laboratory assessments will be collected at screening, and at study visits indicated in the SoA.

Laboratory values from the most recent blood sample collected prior to randomization that are outside the normal range that are suggestive of a disease state (i.e., clinically significant Grade 1 abnormalities or values greater than Grade 1 [refer to Section 10.4]) will lead to exclusion from study enrollment, with the exception of any grade hematuria in a menstruating female, or a urinalysis abnormality judged not clinically significant by the investigator.

Refer to Section 10.4 for toxicity table for grading for each clinical laboratory test.

Clinical safety laboratory parameters that will be evaluated include:

- a. Hematology: Complete blood count (including hemoglobin, platelet count and white blood cell count) and absolute counts for neutrophils, lymphocytes, eosinophils, and monocytes

- b. Serum chemistry: alanine aminotransferase (ALT), aspartate aminotransferase (AST), alkaline phosphatase, total bilirubin, gamma glutamyl transferase (GGT), creatinine, blood urea nitrogen, lactate dehydrogenase (LDH), glucose, albumin, sodium, potassium, chloride, bicarbonate, and calcium.
- c. Urinalysis: Specific gravity, pH, glucose, protein, blood, ketones, bilirubin, urobilinogen, nitrite, leukocyte esterase by dipstick.

Abnormal results and findings that make the participant ineligible for study participation will be discussed with the participant and the participant will be referred for follow-up care with their health care provider if necessary.

All screening laboratory specimens will be processed according to laboratory SOPs available from the clinical laboratory(ies) designated for the study.

All protocol-required safety laboratory tests will be performed by the site local laboratory or at the point of care. Laboratory safety testing performed at point of care will be documented in participant source and captured in the electronic data capture (EDC) database.

Information about the laboratory(ies), including any instructions for performing and interpreting specific tests, will be maintained in the investigator's study files.

The investigator must review the laboratory report, document the review, and record any clinically relevant changes occurring during the study in the AE section of the CRF. The laboratory reports must be filed with the source documents.

All protocol-required laboratory assessments must be conducted in accordance with the Laboratory Manual and the SoA.

If laboratory values from non-protocol-specified laboratory assessments require a change in participant management or are considered clinically significant by the investigator (e.g., AE or SAE), then the results must be recorded in the CRF.

Additional tests may be performed at any time during the study as determined necessary by the investigator or required by local regulations.

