#### **Diagnostic Assessments**

14. Female participants: positive serum pregnancy test
15. Safety laboratory values outside of normal range, for age and sex that are suggestive of a disease state (Grade 1 abnormalities will not lead to exclusion if the investigator considers them not clinically significant.)
16. Urinalysis abnormality greater than Grade 1 (with the exception of hematuria in a menstruating female), or urinalysis abnormality judged clinically significant by the investigator
17. Clinically significant ECG abnormalities
18. Reactive HIV antibody testing
19. Current hepatitis B and/or hepatitis C infection
20. Positive urine drug screen at screening or Day-1 (with the exception of prescribed drugs).

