**Table 10: FDA Toxicity Grading Scale- Urine**

Urine *	Mild (Grade 1)	Moderate (Grade 2)	Severe (Grade 3)	Potentially Life Threatening (Grade 4)
Protein	Trace	1+	2+	Hospitalization or dialysis
Glucose	Trace	1+	2+	Hospitalization for hyperglycemia
Blood (microscopic) red blood cells per high power field (rbc/hpf)	1 - 10	11 – 50	> 50 and/or gross blood	Hospitalization or packed red blood cells (PRBC) transfusion

\* The laboratory values provided in the tables serve as guidelines and are dependent upon institutional normal parameters. Institutional normal reference ranges should be provided to demonstrate that they are appropriate.

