9.2 Clinical Laboratory Evaluations

The following laboratory tests will be performed:

Hematology	Complete blood count (including hemoglobin, platelet count and white blood cell count) and absolute counts for neutrophils, lymphocytes, eosinophils, and monocytes.
Serum Chemistry	Alanine aminotransferase (ALT), aspartate aminotransferase (AST), alkaline phosphatase, total bilirubin, gamma glutamyl transferase (GGT), creatinine, blood urea nitrogen, lactate dehydrogenase (LDH), glucose, albumin, sodium, potassium, chloride, bicarbonate, and calcium.
Urinalysis	Specific gravity, pH, glucose, protein, blood, ketones, bilirubin, urobilinogen, nitrite, leukocyte esterase by dipstick.
Other tests	HIV, hepatitis B and C, urine drug screen, and serum pregnancy test (females only)

The hematology, serum chemistry, and urinalysis tests will be performed at the timepoints indicated in the schedule of assessments (schedule of assessments can be found in [Section 15](#)).

All laboratory values collected at visits will be included in the summaries and listings.

Descriptive summaries of observed value and change from baseline (last result available on or before Day 1) at each scheduled post baseline visit will be presented by treatment group for each continuous parameter for the safety population, both in tabular format and as boxplots. For participants who have an abnormal on-study laboratory result, longitudinal (spider) plots for hematology, serum chemistry, and urinalysis parameters will be produced.

Tables of the worst shift in FDA Toxicity Grading Scale in laboratory values from Day 1 (baseline) to visit Day 8, visit Day 91, visit Day 151 will be also presented per parameter, for those parameters that have FDA Toxicity Grading Scale grading. Values that aren't within any toxicity criteria will be presented as 'Normal'.

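### Urine blood is measured by dipstick but graded in red cells per high-power field, so most positive results have no grade and SAP 9.2, read literally, would show them as 'Normal' in the shift table

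*Protocol*

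**What the plan says.** **Measurement.** Protocol 8.1.7 gives "Urinalysis: Specific gravity, pH, glucose, protein, blood, ketones, bilirubin, urobilinogen, nitrite, leukocyte esterase by dipstick". SAP 9.2 has the same entry: "Specific gravity, pH, glucose, protein, blood, ketones, bilirubin, urobilinogen, nitrite, leukocyte esterase by dipstick". The schedules in Protocol 1.3 and SAP 15 contain a urinalysis row and no urine microscopy.

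**Grading.** Protocol 8.1.7 sends the reader to the appendix tables: "Refer to Section 10.4 for toxicity table for grading for each clinical laboratory test". The urine blood row of Table 10 is headed "Blood (microscopic) red blood cells per high power field (rbc/hpf"). Grade 1 is 1 to 10, Grade 2 is 11 to 50, Grade 3 is "> 50 and/or gross blood", and Grade 4 is "Hospitalization or packed red blood cells (PRBC) transfusion". The protein and glucose rows of the same table use Trace, 1+ and 2+.

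**Presentation.** SAP 9.2 plans worst-shift tables to Days 8, 91 and 151 for parameters that carry an FDA grade, and adds "Values that aren't within any toxicity criteria will be presented as 'Normal".

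**Eligibility.** Exclusion 16 in Protocol 5.2 opens with "Urinalysis abnormality greater than Grade 1 (with the exception of hematuria in a menstruating female") and then adds a second limb that rests on the investigator's judgement of clinical significance.

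**The concern.** The scheduled test and the grading scale are in different units. A dipstick returns an ordered category; the table asks for a cell count, and nothing in either document links the two. For protein and glucose the table already uses dipstick categories, so the mismatch is specific to blood.

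The consequence falls on the secondary laboratory endpoint, which Protocol Section 3 defines by Grade 1 and above. In a first-in-human antibody trial whose aim is descriptive safety, a strip that turns positive after dosing should be visible by treatment group. Under the stated default it may instead carry a label that says nothing was found.

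**Working it through.** The documents give no figure on this point, so the check is a classification exercise followed by a count.

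**Step 1: apply Table 10 and the SAP default to each kind of result.** The only assumption is that the strip reports blood in ordered categories.

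| Result available | Table 10 criterion met | Worst-shift table, read literally |
|---|---|---|
| Dipstick 3+, no visible blood, no microscopy | none | 'Normal' |
| Dipstick 3+ with visible blood | Grade 3 | Grade 3 |
| Dipstick 3+ with admission or transfusion | Grade 4 | Grade 4 |
| Added microscopy, 5 rbc/hpf | Grade 1 | Grade 1 |
| Added microscopy, 30 rbc/hpf | Grade 2 | Grade 2 |

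Grades 1 and 2 and the over-50 part of Grade 3 need a count that the schedule does not produce.

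**Step 2: look for a rule that closes the gap.**

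- The CTCAE v5.0 fallback (Protocol 8.2.3.1 and 10.2.5.1) covers results that Appendix 4 leaves out. Urine blood has a row there, so the fallback does not clearly apply. The SAP shift table uses the FDA scale only.
- Protocol 8.1.7 allows extra tests at the investigator's judgement or where local regulations require them. It does not make microscopy routine after a positive dipstick.
- The Table 10 footnote makes the values guidelines that depend on institutional norms. That can move a limit, but it does not convert a colour category into a count.

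**Step 3: decide whether blood belongs in the shift table.** It has an FDA row, so on a literal reading it is included and the 'Normal' default applies. A programmer who holds that dipstick blood has no usable grade would omit it. The SAP does not settle which. On either reading, a positive dipstick without visible blood is not shown as abnormal in that table.

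**Step 4: see what else in SAP 9.2 would show it by group.** The descriptive summaries and boxplots are for continuous parameters, and a dipstick category is ordinal. The listings and the longitudinal plots for participants with an abnormal result do carry it, but participant by participant. Protocol 9.3.2 promises the frequency of out-of-range results by treatment group; SAP 9.2 specifies no such table, and Protocol Table 7 equates out-of-range with Grade 1 and above.

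**Step 5: count the results exposed.** The Protocol 1.3 schedules have three post-dose urinalyses per participant (Days 8, 91 and 151) in both phases.

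- All participants: 56 x 3 = 168
- RSM01: 48 x 3 = 144
- Placebo: 8 x 3 = 24
- With screening and Day -1 added: 56 x 5 = 280

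These counts assume full attendance. They are results exposed to the gap, not results expected to be mislabelled, because the documents give no rate of positive dipsticks. The shift table classifies participants, so at most 56 participants could be affected.

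**The case against.** Several stronger conclusions might be inferred, and the documents do not support them.

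- *Urine blood can never be graded.* Visible blood is Grade 3 and admission or transfusion is Grade 4, both without microscopy. Unscheduled microscopy is also permitted.
- *A strongly positive result will certainly be shown as 'Normal'.* The default follows a clause limiting the table to parameters with an FDA grade. Omission is a possible reading, and visible blood would be graded.
- *Urine blood is lost from the safety evaluation.* SAP 2.2 states the laboratory endpoint without a grade limit, SAP 9.2 sends all values to summaries and listings, and Protocol 8.1.7 requires clinically relevant changes to be recorded as adverse events.
- *Exclusion 16 and the pausing rule cannot operate on urine blood.* The investigator-judgement limb of exclusion 16 needs no grade. The laboratory pausing trigger in Protocol 7.1.1 requires a related, clinically significant Grade 3 abnormality, which visible blood can reach. Only the grade limb and the numeric part of Grade 3 are affected.

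The Laboratory Manual is not among the documents and may require microscopy after a positive dipstick. If so, grades could be obtained, but the SAP would still need to say which value is graded.

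These points narrow the consequence. They do not remove the mismatch of units or supply a by-group display of dipstick blood.

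**Conclusion.** The point holds in limited form. From scheduled data, a urine blood result short of visible blood, admission or transfusion cannot be graded. Read literally, SAP 9.2 then presents a positive dipstick as 'Normal' in the worst-shift table; on the alternative reading, blood is absent from it. The exposure is 168 scheduled post-dose results, 144 on RSM01, assuming all participants attend. The raw result survives in listings, individual plots and adverse event records, so this is a defect of grading and tabulation rather than a loss of data. It is worth correcting because the correction is cheap and the shift table is the one by-group output in SAP 9.2 that would otherwise be expected to show this result. The conclusion assumes that no document outside the protocol and SAP mandates microscopy and fixes how it is graded.

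**What to change.** In SAP 9.2:

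1. Present urine blood as an ordinal dipstick shift table, baseline to worst post-dose, by treatment group, in the categories that the site's strip reports. Because exclusion 16 exempts hematuria in menstruating participants, some may enter with a positive strip, so the baseline dimension is needed.
2. State that a positive dipstick is never defaulted to 'Normal'. Show it as 'not gradable' unless visible blood, a clinical outcome or an available microscopy value meets a Table 10 criterion.

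Separately, the sponsor should reconcile the measurement method and the grading units across Protocol 8.1.7, exclusion 16 and Table 10. No new grade thresholds are proposed here, since they would feed eligibility and the pausing rule.

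The SAP change costs a short paragraph and one table shell, with no new samples or visits. Any resulting change to the protocol text would be an amendment needing IRB/IEC approval under Protocol 10.1.1; the SAP change need not wait for it.

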### **8.1.8. Pre- and Post-Study Intervention Safety Monitoring**

Participants will remain under observation at the study site for 3 days in the Dose Escalation Phase cohorts (24 hours before dosing and 48 hours after dosing). Participants in the Dose Expansion Phase cohort will present to the study site before the planned Day 1 visit. After treatment on Day 1, the participant will be observed for 4 hours at the study site and may remain overnight based on investigator's decision.

Allergic reactions to RSM01 are possible, therefore, appropriate drugs and medical equipment to treat acute anaphylactic reactions must be immediately available and a physician trained to recognize and treat anaphylaxis must be present in the clinic during study intervention administration and the post-dosing monitoring period.

### **8.1.9. Diary Card, Memory Aid and Daily Monitoring**

#### **Diary card**

Before leaving the clinic after dosing and completion of the post-dosing on-site confinement, participants will be given a diary card and receive guidance on how to fill in the card. All participants will receive a digital thermometer to record temperature. Participants who receive an IM dose will also receive a ruler to measure diameter of redness and/or swelling at the injection site, if present.

The diary card will be used by the study participants to record the duration, and intensity (refer to Section 8.2.3.1) of solicited injection site AEs (for participants who receive an IM dose) and solicited systemic AEs up to Day 7 following injection or infusion for all participants. This information should be recorded in the participant diary card at approximately the same time each evening, through Day 7 (refer to Section 8.2 for more information).

The diary card will be collected and reviewed by the investigator (or designee) on the Day 8 Visit for both the Dose Escalation Phase and the Dose Expansion Phase participants.

No changes to the diary card will be permitted; however, any verbally recalled information provided by the participant during review of the diary card will be documented in the source document and reported as an AE as applicable.

#### **Memory aid**

A memory aid will be utilized by participants to collect unsolicited AEs beginning at discharge from the clinic, through Day 151 (end of study participation for an individual). Participants will be instructed to record unsolicited AEs whenever they occur, recording such AEs on the memory aid. The memory aids will be collected and reviewed by site staff at each subsequent visit through the end of the study.

### **8.1.10. Participant Follow-Up**

Participants will be instructed to contact a study team member to report new or worsening AEs, as well as new diagnoses, and to come to the study clinic if medical attention is needed.

For emergencies and other unscheduled visits to a medical facility other than the study clinic, medical records will, to the extent possible, be obtained by the investigator.

Participants will be asked about the occurrence of AEs, SAEs, AESIs, receipt of concomitant prescription medications/vaccinations, and change in general health status and any other change in status that may affect the participant's participation, as indicated in the SoA.

Any deviation from protocol procedures, evaluations, and/or visits will be documented.

## 8.2. Adverse Events and Serious Adverse Events

Local injection site solicited AEs will include pain, redness and swelling, and will be assessed after dosing at Visit 1 for 7 days (IM recipients only). If more than 1 injection is given, reactions will be assessed separately at each injection site.

Systemic solicited AEs will be assessed in all participants after dosing at Visit 1 and recorded for 7 days. These will include fever, headache, fatigue, muscle aches, nausea, vomiting, diarrhea, and joint pain.

Site staff will document any AEs in the study source during the confinement for all cohorts. The site staff will record solicited injection site AEs (IM doses only) and solicited systemic AEs (all participants), including duration and intensity, during confinement. Refer to Section 8.1.9 for solicited AEs to be recorded in the diary card by participants, through Day 7.

Solicited AEs that continue beyond Day 7 will be captured in the unsolicited AEs memory aid and marked as continuation of solicited AE. Participants will be asked to record events at the same time each evening.

Unsolicited AEs including AESIs, SAEs, and safety laboratory parameters Grade 1 and above will be collected from screening through Day 151 and recorded in the AE log by the study team.

The definitions of AEs, SAEs, serious adverse drug reactions (ADRs) and AESIs can be found in Appendix 2, Section 10.2.1, and 10.2.2, 10.2.3, 10.2.4, respectively.

Refer to Appendix 2, Section 10.2 for details regarding AEs, AESIs, and SAEs and Section 10.4 (Table 9) for laboratory parameters.

Immediate safety concerns should be discussed with the sponsor, and the SRT. The SRT will trigger an IDMC review if any pausing rule is met (see Section 8.2.7 for IDMC and Section 10.2.5 for details regarding AE reporting and follow-up).

AEs will be reported by the participant (or, as appropriate, the participant's legally authorized representative). Clinical chemistry and/or hematology results may also qualify as AEs (Section 10.4, Appendix 4).

Study nurses and physicians are responsible for collecting and documenting information and events that would potentially meet the definition of an AE. However only the investigator or sub-investigator is responsible for assessment, including assignment of causality and, for unsolicited AEs, the intensity, and for reporting and management of all AEs. The investigator is responsible for following up all AEs regardless of their relatedness to study intervention or study procedures, or AEs that caused the participant to withdraw from the study (Section 7).

### 8.2.1. Time Period and Frequency for Collecting AE and SAE Information

Type of Event	Collection Time Period
All solicited AEs	Day 1 through Day 7 (inclusive)
Unsolicited AEs, and SAEs including AESIs	Screening through end of study (Day 151)

Distribution and collection days for diary cards and memory aids are shown in the SoA.

Medical conditions that begin before the start of study intervention but after obtaining informed consent will be recorded on the Medical History/Current Medical Conditions section of the CRF, not in the AE section.

All SAEs and AESIs will be reported to the sponsor or designee within 24 hours, as indicated in Appendix 2, Section 10.2.6. The investigator will submit any updated SAE and AESI data to the sponsor or designees within 24 hours of it being available.

Investigators are not obligated to actively seek AEs, SAEs or AESIs after a participant concludes study participation. However, if the investigator learns of any SAE, including a death, at any time after a participant has been discharged from the study, and he/she considers the event to be related to the study intervention or study participation, the investigator must notify the sponsor or designee within 24 hours.

### 8.2.2. Method of Detecting AEs and SAEs

The methods of recording and follow-up of AEs, SAEs and AESIs are provided in detail in Appendix 2, Section 10.2.5, which includes assessments of intensity, relationship to the study intervention, and outcome of AEs, SAE and AESIs.

Care will be taken not to introduce bias when detecting AEs and/or SAEs. Open-ended and non-leading questions are the preferred method to inquire about AE occurrences.

### 8.2.3. Follow-up of AEs

After the initial SAE/AESI report, the investigator is required to proactively follow each participant at subsequent visits/contacts. All SAEs/AESIs will be followed until resolution, stabilization, or the participant is withdrawn/withdraws, or is lost to follow-up or (as defined in Section 7.2 and Section 7.3, respectively). Refer to Appendix 2, Section 10.2.5.4.

#### 8.2.3.1. AE Intensity

The intensity of AEs will be classified by the investigator based on the toxicity grading tables (Section 10.4 Appendix 4). In the case of an AE or abnormal clinical laboratory result not included in Appendix 4, intensity will be assigned using the Grades described in the U.S. Department of Health and Human Services, Common Terminology Criteria for Adverse Events, Version 5.0 [US HHS 2017] (See Section 10.2.5.1).

Local solicited AEs will be recorded on the diary card by the participant and graded and/or measured by the participant. An exception is that the study investigators will grade solicited AEs

during the confinement period. Any participant-reported Grade 3 or higher adverse event will be assessed by the investigator.

#### **8.2.3.2. AE Causality/Relationship to Study Intervention**

All AEs will be evaluated by the investigator or medically qualified designee (i.e., investigator, sub-investigator) to assess the relationship between study intervention and the AE (with the exception of local injection site reactions, which are assumed to be related to the injection). Careful medical judgment should be exercised to determine the level of causal relationship between an AE and the study intervention. The causality will be assessed as either related or not related.

The sponsor or designee will have the opportunity to confirm the seriousness and case causality based on the clinical judgment of the Medical Monitor or sponsor designee. If a serious adverse event is considered unrelated by the investigator but the sponsor believes that there is a reasonable possibility that the event is related, the sponsor will upgrade the case to a ‘related’ status. The sponsor or designee will never downgrade a case from serious to non-serious or change the investigator assessment of causality from related to not related.

Refer to Appendix 2, Section 10.2.5.2 for details.

